 - It is expected to find improved anthropometrics, decreased fatty mass, and increased fat-free mass in the active arm, when compared to the control arm.
- The changes in quality of life at the end of the study for each group.
 - It is expected to find improvements in quality of life in the active arm, when compared to the control arm.
- Safety of the physical training program, by systematically documenting episodes of variceal bleeding, and hepatic encephalopathy.
 - No increased risk for complications such as GI bleeding and encephalopathy is expected for the active arm with current research design.
- The changes in the metabolic profile (fasting glucose, fasting insulin, lipid profile (total cholesterol, LDL-cholesterol, HDL-cholesterol, triglycerides) at the end of the study for each group.
 - It is expected to have an improved metabolic profile in the active arm, when compared to the control arm.
- The changes in myostatin and insulin-related growth factor 1 (IGF-1) before and after 12 weeks of study.
- In patients undergoing liver transplantation, extension of training program benefits 6 months after liver transplant (reassessment of physical fitness, sarcopenia, anthropometrics, body composition, and metabolic profile).
 - Durability of the beneficial benefits of the training program will be expected across all evaluated variables, with no changes in the control arm after transplant.

RESEARCH STRATEGY

Significance

Unlike other chronic diseases (*i.e.* diabetes mellitus), there are no recommendations for physical training and exercise in patients with cirrhosis. This derives from the fact that there is a paucity of data on the physiologic effects of exercise in patients with cirrhosis and portal hypertension, as well as on the benefits that such training can bring in the long term. Moreover, some safety concerns have been raised in the past particularly with regards to an increased risk for variceal bleeding and HE. Apart from a few pilot studies using supervised exercise as an intervention there are no clinical trials addressing the benefits of an exercise program in patients with ESLD. Furthermore, no study has looked into how a training program can translate into benefits after LT, and since LT patients have a very high risk for metabolic and cardiovascular disease, such a study is highly awaited.

Innovation

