Of the few studies on physical training in cirrhosis there is not a single one balancing the intervention to be effective, reproducible, feasible, and widely available. Moreover, safety has not been systematically investigated. Although supervised exercise at a physical rehabilitation center is effective and reproducible, it is not possible for most patients to join such a program, and these are definitely not widely available. Prior studies using a waist pedometer - a feasible and available design - might have several flaws: failure of the equipment, incapacity to measure all daily activities, lack of knowledge on cardiorespiratory endurance to tailor physical efforts, and no objective measure to assess efficacy of the intervention. Thus, both efficacy and reproducibility are affected.

Current study has a balanced approach: duration and intensity of physical training have been adjusted to provide positive results as based on prior experience (both from supervised and pedometer-based studies), there are objective and accurate evaluations of cardiorespiratory endurance before and after intervention allowing to safely tailor the intensity of physical activities, behavioral modification therapy is included to facilitate changes in lifestyle, relevant safety concerns have been addressed and data will be collected to facilitate further safety refinement, the equipment to be used (bracelet pedometer) has the highest quality and reliability while allowing to correlate effort to changes in heart rate (such as in a supervised exercise program), and we are innovating with the use of PhA and bioimpedance vector analysis to reliably assess changes in body composition. Moreover, in patients undergoing transplantation, post-LT determinations have been considered to investigate duration of the effect in a population that has a very high mortality. Results from present study would provide physiological basis and preliminary results on efficacy and safety in order to develop a multicenter clinical trial aiming to show improved clinical outcomes (survival and dropout from waiting list before LT; survival, quality of life, metabolic and cardiovascular complications after LT) in patients with ESLD, as well as a future policy for exercise training in patients with ESLD.

APPROACH

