All patients referred for an evaluation for liver transplantation, as well as patients with ESLD from hepatology clinics at UAMS, will be screened for study and invited to participate, when applicable. A total of 50 patients will be included in study. Inclusion and exclusion criteria will be as follows:

Inclusion criteria

1. Age 40 to 70.
2. Cirrhosis, any cause, defined as:
 - a. Biopsy-proven.
 - b. Two or more of the following: albumin <3.5 g/dL, INR >1.3, radiologic or endoscopic evidence of portal hypertension.
3. Creatinine <2.0 mg/dL.
4. Physiologic MELD \geq 10.
5. Decompensated cirrhosis with active or history of variceal bleeding, ascites, hepatic encephalopathy, or jaundice.
6. Potential transplant candidate as per UAMS criteria.

Exclusion criteria

1. Large gastric or esophageal varices with contraindication to use beta-blockers.
2. Persistent hepatic encephalopathy grades 2-4.
3. Prior diagnosis of hepatocellular carcinoma, or hepatic hydrothorax (with prior repeated thoracocentesis).
4. Cirrhotic cardiomyopathy or congestive heart failure, pulmonary vascular complications, known active coronary artery disease, syncope, and cardiac dysrhythmias.
5. Physical impediment to perform a cardiorespiratory fitness test.
6. Use of implantable defibrillator or a pacemaker.

Note: all inclusion / exclusion criteria will be obtained from routine investigations available during transplant evaluation, as part of the standard of care.

Description of Study Interventions

Physical Activity

After signing of informed consent patients will be given a Fitbit to measure all physical activity throughout the day. The Fitbit is a digital pedometer inside of a bracelet capable of continuously measuring all physical activities (24/7) and heart rate. Each subject should wear her/his bracelet during the whole duration of the study, for a total of 14 weeks. There will be a 1-week delay between enrollment into the study and the initial study's appointment, in order to obtain the baseline physical activity from each subject (corresponds to week -2, see Study Calendar). Physical activity and heart rate logs will be electronically downloaded to the investigator's computer during each follow up visit.

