The study will occur over a total of 14 weeks, although duration of the intervention will consist of 12 weeks. The first two weeks will serve the purpose of identifying the baseline physical activity of each participant. During the second week all baseline studies/determinations will be completed, with randomization occurring by the end of week 2. Allocation will be stratified by presence or absence of refractory ascites.

Follow up visits for behavioral therapy will occur every 2 weeks for the first 8 weeks, and then on a 4-weekly basis (only active group). Nutritional consultation will occur every 2 to 4 weeks throughout the study (both active and control group). During each visit, the EAA supplement jar will be inspected for percent emptiness (in analogy to a pill count) in order to quantify adherence. Bi-weekly phone calls will be made to all subjects to enhance adherence to recommendations. Standard of care investigations (blood chemistries, hematology and coagulation, liver function tests, etc.) will be ordered according to the needs of the patient and the criteria of the investigator or responsible clinician. Clinical status and complications from portal hypertension, particularly variceal bleeding and HE, will be systematically investigated on each visit.

Research Tests - Variables to Measure

Prior to randomization each subject will be scheduled to undergo all baseline investigations, as follows (see Research Calendar below):

Cardiorespiratory stress test (CRET) and anaerobic threshold (Week -1, Day 1)

CRET will be performed early in the morning on a fasting state, following the maximal incremental cycle ergometry protocol from our Pulmonary Physiology Laboratory, and in agreement with the American Thoracic Society.(38) Briefly, test consists on having the patient on a cycle ergometer performing a progressively increasing work rate until reaching: volitional exhaustion, or termination by the medical monitor. The Borg Rating of Perceived Exertion Scale will be used to help titrate intensity of work rate (aiming for a level of 13 to 17). Gas exchange measurement for

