oxygen uptake and carbon dioxide outflow will be performed during the test, in order to determine VO_2 (oxygen consumption) and VCO_2 (carbon dioxide consumption) in real time. The $\text{VO}_{2\text{max}}$ will be identified as a clear plateau in the VO_2 curve. In cases where no plateau can be observed due to exhaustion, the $\text{VO}_{2\text{peak}}$ at the time of test termination will be used as an equivalent. The anaerobic threshold will be identified by means of the V-slope method on the VO_2 to VCO_2 plot (respiratory exchange ratio).(38) Thirty minutes after completion of the test, each patient will be clinically evaluated for clinical signs of HE according to standard criteria (Table 1 and Figure 2). This test will be repeated after completion of the study period (12 weeks), and 6 months after LT.

Ammonia and lactate thresholds (Week -1, Day 1)

In order to obtain frequent venous samples, an 18-20 Ga IV catheter with a saline lock will be placed in the forearm before the test. Ammonia levels will be determined on venous samples with an automated point-of-care device (PocketChem Ammonia Checker II, Arkray Inc., Kyoto, Japan), prior to the start of the test, and then repeated every 3 minutes until termination of test, with a final sample 20 minutes after termination of the test. This will allow identification of the ammonia threshold when results are plotted against % $\text{VO}_{2\text{max}}$. After a baseline determination of lactate, repeated samples will be obtained every 2 minutes, immediately after the test is finished, and 20 min after termination. This will allow correlating the anaerobic threshold obtained from the respiratory exchange ratio with the lactate threshold. For both the ammonia and lactate thresholds is it estimated that 6-7 blood draws will be performed per patient (4 mL per sample) corresponding to 24-28 mL in total. These two tests will be repeated after completion of the study period (12 weeks).

Six-minute walk test (6MWT) (Week -1, Day 3)

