The questionnaire Sickness Impact Profile (SIP) will be used to assess changes in the quality of life. Recent evidence suggests SIP to be superior to SF-36 in detecting health-related quality of life changes occurring in patients with ESLD. Metabolic profile will include determinations of fasting glucose, insulin (in subjects without diabetes mellitus), lipid profile (triglycerides, total-cholesterol, HDL-cholesterol, LDL-cholesterol), and HbA1c. Both SIP and the metabolic profile will be repeated after completion of the study period (12 weeks). The metabolic profile will be repeated 6 months after LT as well.

Randomization

Each participant will be randomly assigned to the active (physical activity + behavioral therapy + nutritional intervention) or control (nutritional intervention) group. The random allocation sequence will be generated using computer-generated random numbers. There will be no stratification in the randomization process, and allocation will be concealed.

Statistical analysis

Subjects sample has been defined by convenience, as there is no precedent for sample estimation. Descriptive statistics will include mean \pm SD and/or median (range), according to distribution of data. Shapiro-Wilk test will be used to assess normal distribution. Results on VCO₂ will be plotted against VO₂, whereas lactate, and ammonia will be plotted against VO_{2max}, for all patients as an aggregate. The lines determining the anaerobic, lactate, and ammonia thresholds will be calculated by linear regression. Continuous variables comparisons within groups will be done with paired t-test or Wilcoxon, whereas between groups will be done with t-test or Mann-Whitney. Categoric variables will be compared with chi-square or Fisher's exact test, as appropriate. Agreement between methods used to address body composition, bioelectrical impedance and DXA, will be investigated with Bland-Altman test.

Data collection and handling

Title: A physical activity program in end-stage liver disease
PI: [name]

Apart from the data generated by the study demographics and clinical information to properly classify the hepatic functional and cardiorespiratory status of each participant will be retrieved from the electronic medical record (EMR). Such information will include results from standard of care laboratories, imaging, and other special studies (EGD, pulmonary function tests, echocardiogram), to calculate MELD score, and Child-Turcotte-Pugh scores.

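### The safety aim expects no increased bleeding or encephalopathy, but the only planned method that fits is a chi-square or Fisher test, and at 25 per arm a non-significant result cannot support that expectation

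*Combined protocol and SAP*

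**What the plan says.** Under Specific Aims, safety of the training programme is a secondary aim, to be met by "systematically documenting episodes of variceal bleeding, and hepatic encephalopathy". The expectation attached to it is comparative: "No increased risk for complications such as GI bleeding and encephalopathy is expected for the active arm with current research design". Follow Up has these complications looked for at every visit.

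The Statistical analysis section does not mention safety. It lists descriptive statistics, paired and unpaired t-tests with rank alternatives, linear regression for the exercise thresholds, Bland-Altman agreement, and one sentence for categorical data: "Categoric variables will be compared with chi-square or" Fisher's exact test. It plans no confidence interval, gives no margin, and does not say whether patients or episodes are compared.

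On size, 50 patients are to be split equally, and the section says: "Subjects sample has been defined by convenience, as there is no precedent for sample estimation". Under Innovation, the study is meant to give "preliminary results on efficacy and safety in order to develop a multicenter clinical trial".

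**The concern.** The stated expectation is that a difference is absent. Chi-square and Fisher tests look for evidence that a difference is present. When events are few and arms are small, they will usually be non-significant whether or not an excess exists, so the p-value says little about the expectation.

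The users of these data are the designers of the later multicentre trial. They need to know how large an excess the results still allow, and a p-value does not tell them.

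The unit of analysis adds to this. Episodes are to be documented, and a patient may have several, whereas a two-by-two test needs one outcome per patient. The trial enrols patients with "Decompensated cirrhosis with active or history of variceal bleeding, ascites, hepatic encephalopathy, or jaundice", so recurrence is plausible even though persistent encephalopathy of grades 2 to 4 is excluded. Stating the unit in advance removes a choice that could otherwise be made after the data are seen.

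**Working it through.** **No plan figure to reproduce.** The sample is one of convenience. The documents give no alpha, sidedness, power, event rate or dropout.

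**Inputs from the documents.** 50 patients, half per arm, so n = 25 per arm; a 12-week intervention; chi-square or Fisher for categorical data.

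**Assumptions, not in the documents.** Two-sided 0.05, 95% intervals, no dropout, control risk 0% to 20%, and a true excess of 20 points for illustration.

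**1. Chance that Fisher's test detects a 20-point excess.** Power is the sum of Bin(a; 25, pA) × Bin(c; 25, pC) over all pairs with a > c and Fisher p ≤ 0.05, where a and c are the numbers of active and control patients with an event.

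| Control risk | Active risk | Fisher power |
|---|---|---|
| 0% | 20% | 38% |
| 5% | 25% | 37% |
| 10% | 30% | 30% |
| 15% | 35% | 25% |
| 20% | 40% | 23% |

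If uncorrected chi-square replaces Fisher whenever all expected counts are at least 5, the range is 35% to 41%. The conclusion is the same.

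**2. Where the Fisher boundary lies.** For 5 v 0 patients, p = 2 × C(25,5)/C(50,5) = 2 × 53,130/2,118,760 = 0.0502, which is not significant. For 6 v 0, p = 0.022. Against no control events, six active patients must have an event before the test reaches 0.05.

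**3. What a null-looking result leaves open.** Take 2 v 2 patients. Fisher p = 1.0 and the risk difference is 0. The Wilson 95% limits for 2/25 are 0.022 and 0.250. The Newcombe upper limit for the difference is √[(0.250 − 0.080)² + (0.080 − 0.022)²] = 0.179. The Miettinen-Nurminen upper limit is 0.185. An excess of about 18 points is not excluded.

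Other equal splits, all with p = 1.0:

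| Patients with events | Newcombe upper limit | Miettinen-Nurminen upper limit |
|---|---|---|
| 0 v 0 | +13.3 points | +13.6 points |
| 2 v 2 | +17.9 points | +18.5 points |
| 5 v 5 | +22.1 points | +23.1 points |

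**4. Zero events in one arm.** The exact upper limit is 1 − 0.025^(1/25) = 0.137, so 0/25 is compatible with a risk of up to 13.7% in that arm.

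**5. What the proposed interval would show if there were no excess.** With true risks of 5%, 10% or 20% in both arms, the median Miettinen-Nurminen upper limit is +16.3, +18.5 or +23.1 points.

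**The case against.** The strongest reply is that no faulty inference is planned. The protocol states an expectation, with no non-inferiority claim, margin or decision rule. It describes documentation of events, declares a convenience sample and calls its results preliminary. No interval is planned for any endpoint, and a reader given patient counts by arm could compute one. All of this stands, and it limits the weight of the point. It does not remove it: a comparative expectation is stated, the only fitting method cannot support it, and the unit has to be fixed before the data are seen.

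A reader might infer several stronger things that the documents do not support:

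- *That 50 patients is an error.* The documents promise no power for safety, so the power figures show only what a non-significant test can mean.
- *That the team intends to read p>0.05 as proof of safety.* Nothing says so.
- *That events before randomisation will be counted.* After each CRET, including the baseline one, "each patient will be clinically evaluated for clinical signs of HE according to standard criteria". That baseline check precedes allocation, "with randomization occurring by the end of week 2". But the aim concerns the 12-week programme and compares arms that do not yet exist at that point, so counting after randomisation is already implied. Writing it down is still useful.
- *That episodes will be divided by the number of patients.* That table would be invalid, and no section plans it.
- *That events will be sought less often in controls.* Only the behavioural visits are restricted to the active arm. Nutritional consultations and bi-weekly calls cover both arms. At most this needs clarifying against the Study Calendar.

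**Conclusion.** The point holds as an inexpensive improvement to an exploratory secondary aim. The plan offers only a difference test for an expectation of no increased risk. At 25 per arm, a non-significant result leaves excesses in the region of 13 to 23 points open even when the arms have identical counts (0 v 0 to 5 v 5). The detection figures of 23% to 38% rest on the assumed alpha, control risks, 20-point excess and absence of dropout. The interval limits and the 13.7% bound need only the 25 per arm and the 95% level. An interval adds no power; it shows what the trial has not excluded.

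**What to change.** Add a short safety paragraph to the Statistical analysis section:

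- Analyse bleeding and hepatic encephalopathy separately.
- Report by arm, among all randomised patients, the number with at least one new event from randomisation to week 12.
- Give the risk difference (active minus control) with a score interval such as Miettinen-Nurminen, or an exact interval, at 95%.
- List episode counts descriptively.
- Word the safety conclusion as the excess that the interval does not rule out. State that a non-significant p-value is not evidence of no increased risk.

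The paragraph should also say what counts as a new event in a patient who already has encephalopathy at baseline, and how patients who are transplanted, die or leave before week 12 are handled.

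The cost is a few sentences, with no extra patients or tests. The downside is a less favourable safety statement, because at this size the upper limit will usually stay well above zero even with no true excess. With the patient as unit, recurrence is described but not compared.

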Patients with end-stage liver disease (ESLD) have poor physical fitness and muscle wasting (sarcopenia). Both conditions have been associated with elevated mortality before and after liver transplantation (LT). Limited data have shown that exercise benefits patients with chronic liver disease/cirrhosis, however, there are no studies with ESLD patients potentially eligible for LT. Effectively improving physical fitness and sarcopenia in ESLD should positively impact clinical outcomes before/after LT. The primary aim of this study is to improve both physical fitness and sarcopenia in ESLD patients through a 12-week physical training program. Secondary aims will focus on changes in anthropometrics, body composition, quality of life, and metabolic profile. This is a randomized clinical trial including 50 patients, with half allocated to the active group (physical training program) and half to standard of care. Physical training program will consist on achieving $\geq 10,000$ steps/day with an increase of ≥ 4000 above the baseline, facilitated by the feedback from daily step counts and behavioral modification therapy (favoring change towards a more active lifestyle). All participants will have to wear a pedometer bracelet (Fitbit) throughout duration of study (reads blinded to controls), and will receive a daily essential amino acid (EAA) supplement containing approximately 2.25 g of L-leucine along with nutritional consultation. Cardiorespiratory exercise test (CRET), 6-minute walk test (6MWT), and abdominal CT scan will be performed in all participants before and after the period of study to assess for physical fitness and sarcopenia. Anthropometrics, bioelectrical impedance, whole-body DEXA scan, sickness impact profile questionnaire, and the metabolic profile will be obtained at baseline and after completion of the study as well. Blood EAA levels, myostatin, and insulin-related growth factor-1 will be determined at baseline, and at week 12 of study. Durability of changes 6 months post-LT will be assessed as well, when applicable.

INTRODUCTION

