
Remarkably, branch-chained fatty acids (particularly L-leucine) administration has been recently associated with decreased skeletal muscle autophagy and reversal of protein-breakdown signaling. Myostatin is one of the main players driving autophagy and blocking protein synthesis through inhibition of the mammalian target of rapamycin, and it has been found to be elevated in patients with cirrhosis. It is thought that hyperammonemia increases myostatin, then facilitating to impaired proteostasis with the end result of muscle loss or sarcopenia.(26) Finally, insulin-like growth factor 1 (IGF-1) is a trophic factor directly affecting muscle growth and repair, and it is known to be induced with exercise and L-leucine supplementation (Church. J Am Coll Nutr 2016;in press).

Although physical fitness is a modifiable risk factor, there are no studies to date assessing whether an exercise program aiming to improve cardiorespiratory endurance and physical fitness while on the waiting list could potentially improve posttransplant outcomes. One of the concerns with an exercise program in patients with cirrhosis and ESLD is its safety. Two of the perils that could possibly occur as a consequence of exercise are episodes of gastrointestinal (variceal) bleeding and/or HE. Although there are pathophysiologic and anecdotic evidence supporting that an increased risk for these complications is plausible, there are no clinical data to substantiate the concept. At least 9 published studies(4, 5, 11, 25, 27-30) have subjected patients with cirrhosis (\pm ESLD) to physical activity programs or exercise stress testing - intensity varying from a daily low intensity (estimated $VO_{2\max}$ of 35-50%) to a single bout of moderate-to-high intensity exercise ($VO_{2\max}$ 60-100%) - with no documentation of adverse reactions. Particularly no episodes of variceal bleeding or HE were observed. However, it is unknown whether such complications were intentionally investigated in any of the above-mentioned studies, as none of them was designed to identify and correlate such complications of ESLD to physical activity.

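### The myostatin and IGF-1 aim is worded as a before-after change with no comparator, though both arms take a leucine supplement that the protocol says induces IGF-1

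*Combined protocol and SAP*

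**What the plan says.** **The aim.** Under Specific Aims, the secondary aim for these two markers is "The changes in myostatin and insulin-related growth factor 1 (IGF-1) before and after 12 weeks of study". No expectation follows it.

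**Its neighbours.** The threshold, anthropometric and body-composition, quality-of-life and metabolic aims all refer to each group, and each carries an expectation line. The metabolic one is "It is expected to have an improved metabolic profile in the active arm, when compared to the control arm".

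**What the arms share.** The opening summary says that all participants "will receive a daily essential amino acid (EAA) supplement containing approximately 2.25 g of L-leucine along with nutritional consultation". The Randomization section states: "Each participant will be randomly assigned to the active (physical activity + behavioral therapy + nutritional intervention) or control (nutritional intervention) group". The supplement is described under Nutritional Intervention, so it belongs to both arms. What differs is physical activity and behavioral therapy.

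**What the protocol says about leucine.** The Introduction says of IGF-1 that "it is known to be induced with exercise and L-leucine supplementation". It says that branched-chain compounds, L-leucine in particular, have effects on muscle: their "administration has been recently associated with decreased skeletal muscle autophagy and reversal of protein-breakdown signaling". It names myostatin as a main driver of autophagy. On what raises myostatin it says: "It is thought that hyperammonemia increases myostatin".

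**The tests.** The Statistical analysis section says: "Continuous variables comparisons within groups will be done with paired t-test or Wilcoxon". The same sentence gives a t-test or Mann-Whitney for comparisons between groups. Neither is tied to a particular aim, and the section does not say whether the between-group test uses the change or the week-12 value.

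**The concern.** The list of secondary aims is introduced as what the training program will look into. A reader who takes this aim literally would test the change from baseline to week 12, in the active arm or in everyone together, and present the result as an effect of the program.

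That contrast mixes several things. In the active arm it contains training, the supplement, the dietary advice and the passage of time. In the control arm it contains all of these except training. For IGF-1, the protocol itself gives a reason to expect movement without training. For myostatin the reason is more general: a change over 12 weeks without a comparator has no single cause.

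The Innovation section says that the trial is meant to supply a physiological basis for a later multicenter trial. A marker change wrongly credited to training would weaken that basis.

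**Working it through.** **1. Figure in the plan.** There is no power calculation to reproduce. The sample of 50, half per arm, is one of convenience, and the plan gives no SD, effect size or alpha.

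**2. What each contrast estimates.** Write S for the shared effect of supplement, dietary advice and time, and T for the effect of the training package.

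- Change in the active arm: S + T
- Change in the control arm: S
- Change in all 50 pooled: S + T/2
- Difference between arms: (S + T) − S = T

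Only the last is free of S, whatever the size of S.

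**3. Illustration of the size.** Assumptions, none of them in the documents: two-sided alpha 0.05; normal data; 25 per arm with complete data; T = 0; and S equal to d SDs of the change in both arms. Power of the paired t-test is P(|t′| > t_crit), where t′ is noncentral t with n − 1 degrees of freedom and noncentrality d√n. With n = 25 and d = 0.3 the noncentrality is 0.3 × 5 = 1.5 and the critical value is 2.064, which gives 0.302. With p the one-arm power, the chance that the active arm is significant and the control arm is not is p(1 − p), for example 0.302 × 0.698 = 0.211.

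| d | Active arm, n = 25 | Pooled, n = 50 | Active significant, control not | Between arms |
|---|---|---|---|---|
| 0.2 | 16% | 28% | 13% | 5% |
| 0.3 | 30% | 55% | 21% | 5% |
| 0.4 | 48% | 79% | 25% | 5% |
| 0.5 | 67% | 93% | 22% | 5% |

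A simulation of 20,000 trials at d = 0.5 gave 67.1% for the active-arm test and 5.0% for the between-arm test.

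**4. Precision given up.** With the SD of change set to 1, the standard errors are √(1/25) = 0.200 for one arm, √(1/50) = 0.141 pooled, and √(2/25) = 0.283 between arms. The between-arm value is 1.41 times the one-arm value and twice the pooled value. The difference detectable with 80% power is 0.283 × (1.960 + 0.842) = 0.79 SD by the normal approximation and 0.81 SD by the t distribution. Power for a true training effect is 18% at 0.3 SD, 41% at 0.5 SD and 79% at 0.8 SD.

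**5. What baseline adjustment returns.** Assume equal SDs at both visits and a baseline-to-week-12 correlation r. In units of the week-12 variance, the between-arm comparison has variance proportional to 1 on week-12 values, 2(1 − r) on change, and 1 − r² with baseline adjustment. Since 1 − r² ≤ 1 and (1 − r)(1 + r) ≤ 2(1 − r), adjustment is never worse than either, apart from one degree of freedom.

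**The case against.** The strongest reply is that the plan already contains the right comparison. The Statistical analysis section gives a between-group test for continuous variables, these markers are continuous, and the control arm takes the same supplement. On this view the aim only names the two sampling times, as the Blood Biomarkers section does, and the missing expectation line merely marks an exploratory endpoint. Much of this stands. A reader might infer that the plan as a whole is limited to before-after comparisons, or that the design cannot separate training from the supplement; neither is so. What remains is that the paired and between-group tests are listed side by side, nothing says which answers this aim, and the only wording specific to it describes a before-after change.

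A reader might also infer that the protocol says leucine moves both markers. It says so for IGF-1 only. For myostatin it ties leucine to autophagy and protein-breakdown signaling, and names hyperammonemia as the suspected cause of a raised level. A leucine effect on myostatin would be an inference.

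Third, no text states that an active-arm or pooled change will be reported as a training mechanism. That is a risk left open by the wording, not a documented intention.

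Finally, the start of the supplement relative to the baseline sample is not stated outright. The Study Calendar, as extracted, marks the marker samples at weeks 0 and 12 and the first supplement count later, which suggests that the exposure falls between the samples but does not prove it.

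**Conclusion.** The point holds as a gap in the contrast written for one secondary aim. A before-after change in IGF-1 cannot be attributed to training, because by the protocol's own account the shared supplement can produce it. A before-after change in myostatin cannot be attributed to training either, because supplement, dietary advice and time are not separated from it; the protocol does not claim that leucine alters its level.

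The conclusion does not depend on the size of the shared effect, since that effect cancels only in the between-arm difference. The percentages do depend on it. They are illustrative, rest on an assumed shift, alpha and full follow-up, and should not be read as this trial's error rate. They would apply only if the planned between-group test were set aside for this aim.

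The point is minor. It concerns a secondary biomarker aim and does not affect the measures or conclusions of the primary aims.

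**What to change.** Reword the aim so that it is answered by the difference between active and control arms in myostatin and in IGF-1 at week 12, adjusted for the baseline value. Add a sentence to the Statistical analysis section naming the method: ANCOVA with the baseline value as covariate, on a transformed scale such as the logarithm if the marker is skewed.

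Report within-arm changes as descriptive only, labelled as the combined effect of supplement, dietary advice and time, plus training in the active arm, and draw no conclusion about training from them.

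The change takes two sentences. The plan already schedules both blood samples without restricting them to one arm, so no new visit or assay is needed. The real cost is precision: about 0.8 SD is detectable with 80% power at 25 per arm before baseline adjustment, and more than that if patients drop out. The write-up should therefore give the estimate with its confidence interval and not treat a non-significant difference as evidence of no training effect.
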